2.2.4 Missing data

Missed weekly ACD visits will be accounted for by using person-weeks at-risk. If an ACD child does not have a documented visit during a 7-day period, this will be considered a missed person-week at-risk. Missed visits may be due to the child not being present (school, travel, etc..), refusal, or incomplete data entry in the REDCap instrument. Participants can enter the cohort and exit the cohort as described in 2.1.2, and this will be accounted for using person-time at-risk as well.

2.3 Tertiary and exploratory analyses

2.3.1 Tertiary clinical/parasitological endpoints

- 2.3.1.1 Drug resistance mutations The prevalence of parasite mutations associated with reduced susceptibility to antimalarials used both for treatment and prevention will be compared between intervention and control arms. These include mutations in transporters *Pfcrt*, *Pfmdr1*, and antifolate pathways (*DHFR* and *DHPS*).
- 2.3.1.2 Prevalence of anemia- IVM may improve anemia by reducing malaria and/or soil-transmitted helminths in the intervention populace. Changes in the prevalence of anemia will be compared between 1) ACD children in the intervention and control villages; 2) individuals in cross-sectional HHs in the intervention and control villages.

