**Table 3: Summary of the study groups and schedule for blood sampling.**

Group	Number to sample	Ages	What and when samples collected				
			BS=blood smear FP=filter paper	BS&FP -when malaria diagnosed	BS&FP -before season	BS&FP -between the second and third MDA each season	BS&FP -dry season/ post intervention (only from select participants)
Child cohort (followed with active case surveillance)	~1800	≤10 yr. olds	BS&FP -when malaria diagnosed	BS&FP -before season	BS&FP -between the second and third MDA each season	BS&FP -post season	BS&FP -dry season/ post intervention (only from select participants)
Households# on village transects (3 villages/arm; ~8 households/village)	~380	all note: ≤10 yr. olds will be sampled in the ACD cohort		BS&FP -before season	BS&FP -between the second and third MDA each season	BS&FP -post season	BS&FP -dry season/ post intervention
PK-PD modeling cohort	180	5-10yo (n=30 per arm) 11-18yo (n=30 per arm) ≥19yo (n=30 per arm)	Each participant sampled for capillary blood up to 5 of the following time points after their last dose of IVM: 0h (pre-last dose), 1h, 4h*, 8h, 12h*, 24h, 48h, 52h, 60h, 72h, 7d*, 14d, 21d and 28d. *venous blood will be collected simultaneously at these time points				

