# Hemoglobin analyses will also be performed on the capillary blood from a sub-sample of adults and children over the study using a Hemocue (or other) device.							

Trial monitoring will be according to the Data Safety and Monitoring Plan and an independent Data Safety and Monitoring Board (DSMB) will be established by the DMID to provide safety review and trial guidance, including advice on continuing, modifying or terminating the study. The study monitor will be an in-country contract research organization (CliMAfrica-CRO or other) who will provide external monitoring for the study. During the intervention phase, trained clinical trial monitoring experts from the CRO will conduct at least six monitoring visits (before, during and immediately after the intervention phase of the study, in rainy seasons 1 and 2). These will include assessment of site compliance and standard operating procedures, review of consents, assents, training documents, research/study approvals and data collection forms, review of site facilities, and laboratory sample storage, shipment, and labeling. An interim analysis of the safety data will be conducted after the 2nd MDA occurs in the first rainy season, and also in-between the first and second rainy seasons.

---

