## 10.2. Sample Size Considerations

[figure not shown]
The trial design and power calculation is guided by the Malaria Transmission model developed at Imperial College, London (<http://www.imperial.ac.uk/malaria-modelling/tools-and-data/>) and informed by data from our RIMDAMAL I trial as well as the longer mosquitocidal effect (up to 30 days) from the intervention dose and regimen predicted from IVERMAL data. The model suggests we should observe an effect size in the intervention arm over the control arm of 43.1% (Figure 4). This assumes a rate incidence in our 0-10 yr. old cohort of 1.088 malaria episodes/child/year and 0.619 malaria episodes/child/year in the control and intervention arms, respectively. To determine the cluster sample size and cluster population (children cohort size) we used the sample size formula for obtaining the number of clusters in an unmatched CRT design with a 'rate' endpoint (49). The formula uses the coefficient of variation ( $\kappa$ ; SD/mean) of the true rates between clusters within each group, which we estimated in southwestern Burkina Faso to be 0.258 (50). From these variables, and setting the  $\alpha=0.05$  (Type I error rate or probability of detecting a false negative result = 1.96), 6 clusters/arm with a minimum of 48 children/cluster in our child cohort is necessary to detect a significant difference in the rates between the arms with 80% power (Type II error rate or probability of rejecting a false positive result = 0.84). Relatedly, if we instead calculate the cluster population sample size using the intraclass correlation coefficient retrospectively calculated from RIMDAMAL I data (ICC=0.059), and setting the  $\alpha=0.05$ , with 6 clusters/arm the necessary number of children to follow per cluster is 9.

In January 2019, the sample size modeling exercise was re-performed because it was learned that that villages in the Diebougou health district (the study site) were expected to receive new Interceptor G2 LLINs prior to the 2019 rainy season. These new LLINs are made with two different insecticides (chlorphenapyr and alpha-cypermethrin) to circumvent the prevalent pyrethroid-resistance seen in Burkina Faso the much of SSA. Thus, we assumed a 12%-50% reduction in malaria incidence in

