#### 10.4. **Final Analysis Plan**

The final statistical plan will be written in detail in the finalized standard operating procedure, before the start of the intervention phase, to ensure that the sampling plan (e.g. number of nurse visits, number of mosquitoes and blood samples) collected are appropriate for the intended analyses. In general, standard, two-tailed statistical hypothesis testing  $\alpha=0.05$ , as well as estimating and comparing the effect sizes and confidence intervals, will be used to measure the differences in entomological and parasitological secondary outcomes between arms. The tests used will depend on the type of data collected (e.g., survivorship of blood fed mosquitoes in each arm per collection interval, proportion of mosquitoes parous/arm per collection interval, average counts of trophozoites/slide or counts of the parasite molecular force of infection, sporozoite rates in mosquitoes), and their distributions. These data will also be used to make generalized linear and non-linear mixed effects models in R, SAS or other programs to understand the functional relationships of measured entomological and parasitological variables and the relative contributions of various independent variables on variation in the dependent variable.

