5. APPENDIX: FUTURE WORK TO BE CONSIDERED

- 1. Pharmacokinetic/dynamic parameters
 - a. Impact of age on IVM PK
 - b. Evaluation of IVM metabolites
 - c. Relationship of IVM PK with blood-feeding results done at CSU
 - d. Safety of IVM (clinical, hematology, chemistry)
 - e. Comparison on capillary and venous measurements of IVM

2. Parasite data

- a. Parasitemia [Count data] done by quantitative PCR compare (log10) distributions in populations between arms
 - i. SMC-treated only
 - ii. IVM/placebo-treated only
 - iii. all cohort
- b. Multiplicity of Infection (MOI) per episode or sampling timepoint and molecular Force of Infection (mFOI) per child [Count data] done by either genotyping microsatellites or amplicon deep sequencing
 - i. Regression analysis with Poisson distribution, in an unadjusted analysis followed by an adjusted analysis taking into account the random effects of the cluster (village) and household and fixed effects such as sex, LLIN use, age, and treatment with SMC or IVM.

3. Entomology data

- a. Survivorship bioassays of blood fed mosquitoes [Survival assays]
 - i. Consider time variable
- b. Catch density [count data]
 - i. Consider time variable
- c. Age structure
 - i. Age distribution of mosquitoes in Intervention vs. Control clusters
 - ii. Proportion of mosquitoes caught over an age cut-off (>10 days)
 - 1. Consider time variable
- d. Proportion of mosquito blood meals taken from humans vs other animals
 - i. Consider time variable
- e. Proportion of mosquitoes with sporozoites
 - i. Consider time variable
- f. Entomological inoculation rates (human biting proportion x sporozoite rate)
 - i. Consider time variable

4. Other studies

- a. Impact of IVM on the prevalence of drug and insecticide resistance
- b. Impact of IVM on all-cause anemia in children
- c. Household survey association of household factors and vector density

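### Haemoglobin is measured as a number but compared between arms only as anaemia yes/no; adding a haemoglobin model would be a cheap gain for a tertiary endpoint

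*SAP*

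**What the plan says.** SAP 2.3.1.2 lists anaemia as a tertiary endpoint, on the reasoning that ivermectin "may improve anemia by reducing malaria and/or soil-transmitted helminths in the intervention populace". The comparison it names is of prevalence: "Changes in the prevalence of anemia will be compared between 1) ACD children in the intervention and control villages; 2) individuals in cross-sectional HHs", by arm. It gives no cut-off, model or covariates.

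The measurement is described in the footnote to Table 3 of the protocol (section 4): "Hemoglobin analyses will also be performed on the capillary blood from a sub-sample of adults and children over the study using a Hemocue" or another device. The footnote marker sits on the row "Households# on village transects (3 villages/arm; ~8 households/village", which has about 380 people in total. The size of the haemoglobin sub-sample among children in the active case detection (ACD) cohort is not stated.

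Anaemia appears twice more in the SAP: as a single word among the additional figures and tables in section 3, and in the future-work appendix as "Impact of IVM on all-cause anemia in children". Neither entry says what form the outcome takes. Separately, the PK/PD cohort has full blood counts (protocol 7.10.1.1), and the SAP appendix lists haematology among its safety items.

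**The concern.** A Hemocue reading is a value in g/dL. Reducing it to anaemic or not discards how far each person lies from the threshold. Fewer malaria episodes and fewer worms could plausibly move haemoglobin across much of the population, and a threshold is an inefficient detector of that kind of change.

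Information is scarce here: there are 14 villages for the ACD comparison and 6 for the transect households. A real haemoglobin benefit could be reported as no effect on anaemia when the same samples, analysed on their own scale, might have shown it.

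**Working it through.** **The plan's own figure.** No power is stated for anaemia. The only sizing is for the primary outcome, to detect a "difference in the rates between the arms with 80% power". It reproduces with the unmatched rate formula that the protocol cites:

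c = 1 + (1.96 + 0.84)² × [(1.088 + 0.619)/48 + 0.258² × (1.088² + 0.619²)] / (1.088 − 0.619)² = 5.99, that is, 6 villages per arm.

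It says nothing about haemoglobin.

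**Inputs.**
- From the documents: 7 villages per arm with about 100 children each; 3 villages per arm for the transects, 380/6 ≈ 63 people each; "two-tailed statistical hypothesis testing" at 0.05. The one ICC given is 0.059, calculated from the previous trial's malaria data and not from haemoglobin.
- Assumed: normally distributed haemoglobin; a uniform shift sized so that the continuous village-level analysis has 80% power; control-arm anaemia prevalence 20–60%; ICC 0.005–0.10; 20–100 people measured per village.

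**Step 1, information kept within villages.** For a normal variable cut at prevalence p, relative efficiency is RE = φ(z_p)²/[p(1−p)]. This gives 0.49 at p = 20%, 0.58 at 30%, 0.64 at 50% and 0.62 at 60%.

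**Step 2, add clustering.** In units of the total variance, a village mean has variance V = ICC + (1−ICC)/m on the continuous scale and about ICC + (1−ICC)/(m·RE) after the cut. The between-village part is common to both, which shrinks the loss. The noncentrality is multiplied by √(V_cont/V_cut), with 2k−2 degrees of freedom for k villages per arm.

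Example, 7 × 100 at ICC 0.059 and p = 20%:
- V_cont = 0.059 + 0.941/100 = 0.0684.
- V_cut = 0.059 + 0.941/(100 × 0.49) = 0.0782.
- √(0.0684/0.0782) = 0.935.
- With 12 df, 80% power needs a noncentrality of 3.05; 3.05 × 0.935 = 2.86, which gives power of 74.6%. The loss is 5.4 points.
- At p = 50% the multiplier is 0.963 and the loss is 3.0 points.

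**Step 3, simulation.** Village effects and anaemia counts were simulated, with a t-test on village proportions. Points lost from 80%, repeat runs agreeing to about a point:

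| Villages/arm × people | ICC | p = 20% | 30% | 50% |
|---|---|---|---|---|
| 7 × 100 | 0.02 | 15 | 10 | 7 |
| 7 × 100 | 0.059 | 9 | 6 | 3 |
| 7 × 50 | 0.02 | 22 | 15 | 11 |
| 7 × 50 | 0.059 | 14 | 10 | 6 |
| 7 × 20 | 0.02 | 30 | 21 | 15 |
| 7 × 20 | 0.059 | 24 | 16 | 9 |
| 3 × 63 | 0.02 | 23 | 15 | 9 |
| 3 × 63 | 0.059 | 19 | 12 | 5 |

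The simulated losses exceed the Step 2 formula at low prevalence because the shifts needed for 80% power are large, and the formula is a small-effect approximation. Across the whole assumed range the loss runs from about 1 to 33 points, and roughly 2 to 30 covers nearly all of it.

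**Step 4, drop the uniform shift.** Suppose instead that 20% of people have haemoglobin lowered by 2 SD and that the intervention cuts this fraction by 43.1% (the malaria effect size, borrowed for illustration), to 0.20 × 0.569 = 11.4%. Put the cut 1.5 SD below the mean of unaffected people.
- Prevalence falls from 19.2% to 13.8%. Squared difference over summed variances: 0.054²/(0.155 + 0.119) ≈ 0.0106.
- Mean haemoglobin rises by 2 × 0.0862 = 0.172 SD. The same ratio: 0.172²/(1.64 + 1.40) ≈ 0.0098.
- The relative efficiency of the cut is about 1.08, so it loses nothing.

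With lowering of 1.5–2 SD and prevalence of about 15–30%, the efficiency is about 0.9–1.1. With 1 SD and prevalence of 12–23%, it is about 0.7–0.8.

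**The case against.** The strongest reply is that the size of the loss is built from assumptions. The documents supply no haemoglobin SD, effect, prevalence, cut-off, ICC or sub-sample size, and the 80% starting power is imposed. The calculation also treats a single cross-section, while the SAP compares changes. The uniform shift is not stated in the SAP either: it says only that anaemia may improve, and Step 4 shows that a benefit confined to the low tail can leave the cut as efficient as the mean. All of this stands, and it is why the result is a wide conditional range.

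Three stronger readings are tempting, and the documents do not support them.
- A reader might infer a general loss of 10 to 30 points. That fits an analysis ignoring clustering, or one with a very small ICC or few people per village. It does not fit 7 × 100 at ICC 0.059.
- A reader might infer that haemoglobin is examined nowhere. The PK/PD blood counts and the appendix's haematology safety item show otherwise; the gap concerns the ACD and cross-sectional groups.
- A reader might conclude that prevalence should give way to mean haemoglobin. Prevalence is the named endpoint, is clinically readable and answers a different question. Nor does age and sex adjustment require a continuous outcome, since a binomial mixed model can adjust too.

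The reply does not remove the basic point. The numeric value is collected, and no between-arm analysis of it is planned in these two groups. A full 100 children per village is also the favourable case: the protocol speaks of a sub-sample and attaches the footnote to the transect row.

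**Conclusion.** The point holds as a low-impact improvement. If the ivermectin effect is broadly a shift in haemoglobin, analysing only anaemia yes/no costs roughly 2 to 30 points of power against a continuous analysis set at 80%: about 3 to 9 points for 7 villages per arm × 100 children at ICC 0.059, and more with small sub-samples, a lower ICC or lower prevalence. If the benefit sits in the low tail, the loss could be small or absent. The endpoint is tertiary with no power claim, so no stated power and no primary conclusion is affected.

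**What to change.** Keep the anaemia prevalence comparison in SAP 2.3.1.2 as the named endpoint. Add a between-arm analysis of haemoglobin (g/dL), for the ACD children and for the cross-sectional households, by linear mixed model with:
- fixed effects for arm, season, age and sex, and start-of-season haemoglobin where it was measured;
- a random village effect;
- Kenward-Roger degrees of freedom, as in the primary model.

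Report the adjusted mean difference with its 95% CI next to prevalence by arm. The same edit could state the anaemia cut-off and the size of the haemoglobin sub-sample, which the SAP leaves open.

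The cost is a few lines of SAP text and one more model on data already collected, with no new samples or visits. The downsides are one extra tertiary analysis and a mean difference that policy readers know less well than prevalence.

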2.3.2 Tertiary entomological endpoints

- **2.3.2.1** Measures of insecticide resistance- Changes in mosquito phenotypic susceptibility to standard insecticides will be analyzed between times this was tested at the study site and related to the prevalence of mosquito SNPs (or quantity of gene transcripts) that correlate with known, genetic insecticide resistance markers.
- **2.3.2.2** Age structure of the mosquito population over time- This will be defined as the estimated median age of the adult female *An. gambiae* s.l. population per unit time or the proportions estimated in certain age classes per unit time. Estimates will be done with traditional and novel age grading techniques.

2.3.3 Subgroup analysis

- **2.3.3.1** SMC-treated children only incidence will be compared between those children who received SMC only (age 3-59 months)
- 2.3.3.2 IVM/placebo-treated children only incidence will be compared between those children who received MDA/placebo only (≥90 cm and ≤10 y/o)

Other notes regarding covariates/effects to consider:

 Analyze the IRs by cluster and arm over short time periods (by week) for each season using regression approaches

- Malaria transmission intensity naturally varies over each season due to changing weather and mosquito vector species and densities and changing human immunity.
- Each of the 4 ivermectin MDAs per season acts like a "pulse" of insecticidal blood that starts high and then the mosquito-killing efficacy wanes over time as the ivermectin is eliminated from treated persons' blood. We estimate the mosquito killing activity lasts for 2-3 weeks but is highest in the week after the MDA is given. On top of this, there would be a time delay, as the killing would reduce biting, and then a week to 2 later, the numbers of parasitemic individuals would decrease
- Spatial effects between and within clusters
 - The incidence difference based on child/ HH location in cluster inner vs. outer edge of the cluster
 - Differences based on the density of non-study populations nearby (within several km of the cluster boundaries)
- Random effect within HHs in clusters (due to HH size, proportion of males to females in a HH, age proportion in a HH proportion, HH members treated and/or treated over time)

3. PLANNED TABLES, FIGURES, LISTINGS

Manuscript Tables:

- 1. Participant characteristics
- 2. Primary efficacy analyses
- 3. Adverse events
- 4. Subgroup analysis of malaria risk

Manuscript Figures:

- 1. CONSORT diagram
- 2. Map of study area
- 3. Rainfall and weekly malaria incidence

Supplementary appendix tables:

- S2.1: Percentage reduction in clinical incidence during the trial period
- S3.1: Risk in epidemiological strata
- S3.2: Exploratory analysis of the frequency of malaria episodes per child in each group

Figures: Supplementary appendix

- S1.1: Map of study area
- S2.1: Estimated reduction in clinical incidence
- S3.1: Flow diagram for all RIMDAMAL participants with respect to MDA participation and AE analysis.
- S3.2: Weekly malaria incidence per person-year in the RIMDAMAL study cohort children plotted over the study period.

Supplementary appendix Listing:

- S4.1: Descriptions of reported adverse events (AE) in RIMDAMAL villages (excluding uncomplicated malaria recorded from the child cohort.
- S4.2: Summary of deaths during intervention season

Additional figures/tables:

- Seasonality: Risk by month with rainfall
- Interaction of Interceptor G2 bed net distribution by cluster/HH/individual (only in 2020)
- Interaction of proportion of people treated per cluster and over time.
- MOI
- mFOI
- anemia
- entomology outcome figures

5. APPENDIX: FUTURE WORK TO BE CONSIDERED

- 1. Pharmacokinetic/dynamic parameters
 - a. Impact of age on IVM PK
 - b. Evaluation of IVM metabolites
 - c. Relationship of IVM PK with blood-feeding results done at CSU
 - d. Safety of IVM (clinical, hematology, chemistry)
 - e. Comparison on capillary and venous measurements of IVM

2. Parasite data

- a. Parasitemia [Count data] done by quantitative PCR compare (log10) distributions in populations between arms
 - i. SMC-treated only
 - ii. IVM/placebo-treated only
 - iii. all cohort
- b. Multiplicity of Infection (MOI) per episode or sampling timepoint and molecular Force of Infection (mFOI) per child [Count data] done by either genotyping microsatellites or amplicon deep sequencing
 - i. Regression analysis with Poisson distribution, in an unadjusted analysis followed by an adjusted analysis taking into account the random effects of the cluster (village) and household and fixed effects such as sex, LLIN use, age, and treatment with SMC or IVM.

3. Entomology data

- a. Survivorship bioassays of blood fed mosquitoes [Survival assays]
 - i. Consider time variable
- b. Catch density [count data]
 - i. Consider time variable
- c. Age structure
 - i. Age distribution of mosquitoes in Intervention vs. Control clusters
 - ii. Proportion of mosquitoes caught over an age cut-off (>10 days)
 - 1. Consider time variable
- d. Proportion of mosquito blood meals taken from humans vs other animals
 - i. Consider time variable
- e. Proportion of mosquitoes with sporozoites
 - i. Consider time variable
- f. Entomological inoculation rates (human biting proportion x sporozoite rate)
 - i. Consider time variable

4. Other studies

- a. Impact of IVM on the prevalence of drug and insecticide resistance
- b. Impact of IVM on all-cause anemia in children
- c. Household survey association of household factors and vector density
